#### **7.4.2. Interim Analyses and Data Monitoring**

No formal interim analysis or safety monitoring committee is planned for this study.

#### **7.4.3. Final Analysis and Publication of Study Results**

The final analysis will be completed after all subjects have completed the study.

#### **7.5. Multiple Testing Procedures**

There will be no adjustments for multiplicity and no formal multiple testing procedures are to be implemented with this analysis plan.

#### **7.6. Baseline Values**

Baseline values are the values obtained prior to the first study drug administration on Day 1 (scheduled between 8PM and 10PM in the evening). If the Day 1 value is missing, the value at Screening will be treated as the baseline.

## **8. SUMMARY OF STUDY DATA**

### **8.1. Subject Disposition**

A summary of the analysis sets includes the number and percentage of subjects by treatment group and overall for the following categories: subjects in the AR Population, subjects in the Safety Population, and subjects in the FAS Population. All percentages will be based on the number of subjects randomized.

End of trial information will also be summarized in this table, including the number of subjects completing the study, the number of subjects who prematurely discontinued the study with reasons for withdrawal, the number of subjects completing the study medication dosing, and the number of subjects who prematurely discontinued the study medication with reasons for study medication discontinuation.

A by-subject data listing of study completion information including the reason for premature study withdrawal, if applicable, will be presented.

### **8.2. Protocol Deviations**

Major protocol deviations, as determined by a Sponsor blinded review of the data prior to database lock and unblinding of the study, may result in the removal of a subject's data from the PP Population. The Sponsor or designee will be responsible for producing the final deviation file; this file will include a description of the protocol deviation and clearly identify whether this violation warrants exclusion from the PP Population. This file will be finalized prior to database lock.

All protocol deviations will be presented in a by-subject data listing, with a flag to indicate if a deviation was considered major..

### **8.3. Demographics and Baseline Characteristics**

Subject demographic data and baseline characteristics will be tabulated and summarized descriptively by treatment group and overall. The demographic data and baseline characteristics will be summarized for the Safety and FAS Populations.

The demographics and baseline characteristics consist of age (year), sex, race, ethnicity, and study eye (OD [right eye] or OS [left eye]), and baseline IOP category (<25 mmHg or ≥25 mmHg). A subject's age in years is calculated using the date of the informed consent and date of birth. Age will be summarized using descriptive statistics. The number and percentage of subjects by gender, race, ethnicity, study eye, and baseline IOP category will also be reported. Percentages will be based on the total number of subjects in the study population presentation.

The following baseline characteristics will be summarized for OD and OS, and for study eye, fellow eye, and all eyes, using descriptive statistics:

- Pupil diameter, photopic and mesopic
- BCDVA, photopic and mesopic, monocular only
- DCNVA, photopic and mesopic, monocular only
- IOP at 8am, 10am, 4pm, and mean diurnal

All demographic and baseline information will be listed by subject.

#### **8.4. Medical History**

The number and percent of subjects with individual medical histories will be summarized for all subjects by treatment group and overall. Non-ocular and ocular medical history will be summarized separately.

Medical history will be coded using the MedDRA Version 22.0. The number and percentage of subjects with any medical history will be summarized overall and for each system organ class (SOC) and preferred term (PT). Percentages will be calculated based on number of subjects in the Safety Population.

Subject medical history data including specific details will be presented in by-subject listings.

#### **8.5. Prior and Concurrent Medications**

The number and percentages of all concomitant medications will be summarized by treatment group, Anatomical Therapeutic Chemical (ATC) level 4, and PT. The total number of concomitant medications and the number and percentages of subjects with at least 1 concomitant medication will be summarized by treatment group. All summaries will be performed using the Safety Population.

A concomitant medication is defined as any medication taken on or after the day of first exposure to study drug.

Prior medications are defined as any medication that has a start and stop date prior to the day of first exposure to any study drug, collected from up to 30 days prior to Screening.

#### **8.6. Treatment Compliance and Exposure**

Continuous descriptive summaries for total exposure to study drug (in days) and percentage compliance will be presented for the Safety Population by treatment group. Exposure to study drug will be determined by counting the total number of used bottles returned.

Compliance will be determined by calculating the percent of used bottles returned to the total that should have been used during the treatment period.

## 9. EFFICACY ANALYSES

Unless otherwise noted, all efficacy analyses will be completed using the FAS, AR, and PP Populations. The FAS Population will be the primary analysis population for efficacy. All efficacy analyses will be completed using the planned dose that the subject received.

### 9.1. Clinical Efficacy

The evaluations of clinical efficacy will be performed using the FAS, AR, and PP Population, as specified below. Baseline values are generally taken at the Day 1 (Qualification/Baseline) Visit.

IOP, near and distance VA, and pupil diameter will be measured at the Screening Visit, the Qualification/Baseline Visit, the Treatment-study visits, and Follow-up Visit.

**Table 2 Clinical Efficacy Assessments**

Efficacy Assessment	Equipment Name	Measurement (Unit)	Procedure
IOP	[REDACTED]	mmHg	[REDACTED]
Distance VA	[REDACTED]	Letters	[REDACTED]
Near VA	[REDACTED]	Jaeger	[REDACTED]

Pupil diameter		mm	

\*For this study photopic and mesopic light conditions are considered to be “with the lights on or with the lights off”.

IOP measurements at the Baseline Visit and both Treatment-study Visits will be performed at 8AM, 10AM and 4PM. All IOP measurements have a window of  $\pm 15$  minutes with at least 2 hours between the 8AM and 10AM assessments. IOP will be measured twice in both eyes at each timepoint. The mean value at each timepoint for the study eye will be used in efficacy assessments. If the difference in the two IOP measurements is  $> 5\text{mmHg}$ , a third measurement will be obtained, and the three values averaged. Mean diurnal IOP is the mean of the IOP measurements at all three timepoints (8AM, 10AM, 4PM).

Near and distance VA and pupil diameter will be performed in photopic and mesopic conditions. Furthermore, near and distance VA will each be assessed using monocular (OD and OS separately) and binocular (OU [both eyes]) measurements.

Primary Efficacy Endpoint:

The primary efficacy endpoint will be analyzed using ANCOVA with change from Baseline to Day 15 in mean diurnal IOP in the study eye as the dependent variable; treatment as a factor; and Baseline mean diurnal IOP as the covariate. The ANCOVA will be performed using the FAS, with subjects included in their randomized treatment group regardless of the treatment they actually received. The least-squares mean (LSM) and standard error (SE) will be provided for both treatment groups, along with the placebo-corrected LSM (Nyxol – placebo), its 95% confidence interval (CI) and associated p-value.

A confirmatory analysis of the primary efficacy endpoint will be performed, using the AR population with missing Day 15 values imputed. See [Section 7.3.2](#) for imputation methods.

Another confirmatory analysis of the primary efficacy endpoint will be performed using the PP population. No imputation of missing Day 15 values will be applied.

Secondary Efficacy Endpoints:

Secondary efficacy endpoints (for the study eye unless otherwise noted) are indicated in [Section 4.2.2](#). Secondary efficacy endpoints will be analyzed by study eye, fellow eye and all eyes (unless otherwise indicated). "All eyes" refers to the pooled data from the study eye and fellow eye, so there will be 2 results per subject for any summary of all eyes if the endpoint was assessed for both the study eye and fellow eye. Secondary efficacy assessments not related to IOP will be analyzed only at 8AM. Binocular near and distance VA assessments will not be analyzed. All secondary efficacy assessment data, regardless of whether they are included in the analysis, will be presented in by-subject listings.

For each of the continuous secondary efficacy endpoints, the same ANCOVA for the primary efficacy endpoint will be used, with the respective Baseline included as the covariate. Each ANCOVA will be performed using the FAS with subjects included in their randomized treatment group regardless of the treatment they actually received. The output from each ANCOVA will include the LSM and SE for both treatment groups, along with the placebo-corrected LSM (Nyxol – placebo), its 95% CI and associated p-value.

For each of the secondary efficacy endpoints related to percentage of subjects (or percentage of eyes) meeting certain criteria, the analysis will be performed for the FAS using a logistic regression with treatment and Baseline included as independent factors. For each analysis, the percentage of subjects (or eyes) in each treatment group meeting the criteria, the odds ratio (OR) with 95% CI and p-value will be provided.

For the analysis of the secondary efficacy endpoints, only observed case data will be used.

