4. STUDY DESIGN

4.1. Primary and secondary endpoints

Efficacy:

The primary efficacy endpoint is the change from Baseline to Day 15 in mean diurnal IOP in the study eye. Mean diurnal IOP is the mean of the IOP measurements at all three timepoints (8AM, 10AM, 4PM).

ALL TREATMENTS WILL BE ADMINISTERED TO BOTH EYES AND IOP WILL BE MEASURED IN BOTH EYES.

The eye with the higher IOP at the Qualification Visit at 8AM is designated as the study eye. In the case where both eyes have the same IOP, the study eye will be the RIGHT eye. Baseline IOP evaluations will occur before dosing on Day 1. Treatment-study IOP evaluations will occur on Days 8 ± 1 Day and Day 15 ± 1 Day. Follow-up IOP evaluations will occur at $8AM \pm 15$ minutes on Day 16.

IOP measurements at the Baseline Visit and both Treatment-study Visits will be done at 8AM, 10AM and 4PM. All IOP measurements have a window of ± 15 minutes with at least 2 hours between the 8AM and 10AM assessments. IOP will be measured twice in both eyes at all time points. The mean IOP at each timepoint (8AM, 10AM, 4PM) is the average of the 2 IOP measurements at that timepoint. If the difference in the two IOP measurements is > 5 mmHg, a third measurement will be obtained, and the three values averaged.

Secondary efficacy endpoints will be analyzed by study eye, fellow eye and all eyes (unless otherwise indicated) and will include:

- Change from Baseline to Day 15 in mean diurnal IOP in the fellow eye and all eyes.
- Change from Baseline to Day 8 in mean diurnal IOP.
- Mean IOP at each post-treatment timepoint (8AM, 10AM and 4PM; on Day 8 and Day 15).
- Change and percent change from Baseline to Day 8 and Day 15 in IOP at each timepoint (8AM, 10AM, 4PM), and Day 16 at 8AM.
- Percentage of subjects achieving reductions from Baseline to Day 8 and Day 15 in IOP at 8AM of greater than or equal to 10%, 15%, 20%, 25% and 30%.
- Percentage of subjects achieving Day 8, Day 15 and Day 16 IOP levels at 8AM of less than or equal to 16mmHg, 18mmHg, 20mmHg and 22mmHg.
- Change and percent change from Baseline Day 8, Day 15, and Day 16 in IOP at 8AM.
- Change and percent change to Days 8, 15, and 16 in pupil diameter at 8AM.
- Percentage of subjects achieving reductions from Baseline to Day 8, Day 15 and Day 16 in pupil diameter at 8AM, of greater than or equal to 10%, 15%, 20%, 25%, and 30%.

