#### **4.2.2. Secondary Endpoints**

Secondary endpoints for efficacy and safety assessments include the following:

Efficacy:

Secondary efficacy endpoints will be analyzed by study eye, fellow eye and all eyes (the pooled data from the study eye and fellow eye) unless otherwise indicated, and will include:

- Change from Baseline to Day 15 in mean diurnal IOP in the fellow eye and all eyes.
- Change from Baseline to Day 8 in mean diurnal IOP.
- Mean IOP at each post-treatment timepoint (8AM, 10AM and 4PM; on Day 8 and Day 15).
- Change and percent change from Baseline to Day 8 and Day 15 in IOP at each timepoint (8AM, 10AM, 4PM), and Day 16 at 8AM.

- Percentage of subjects achieving reductions from Baseline to Day 8 and Day 15 in IOP at 8AM of greater than or equal to 10%, 15%, 20%, 25% and 30%.
- Percentage of subjects achieving Day 8, Day 15 and Day 16 IOP levels at 8AM of less than or equal to 16mmHg, 18mmHg, 20mmHg and 22mmHg.
- Change and percent change from Baseline Day 8, Day 15, and Day 16 in IOP at 8AM.
- Change and percent change to Days 8, 15, and 16 in pupil diameter at 8AM.
- Percentage of subjects achieving reductions from Baseline to Day 8, Day 15 and Day 16 in pupil diameter at 8AM, of greater than or equal to 10%, 15%, 20%, 25%, and 30%.
- Change from Baseline to Day 8, Day 15, and Day 16 in best corrected distance visual acuity (BCDVA) (Early Treatment Diabetic Retinopathy Study [ETDRS] high contrast) (photopic and mesopic) at 8AM.
- Change from Baseline to Day 8, Day 15, and Day 16 in distance corrected near visual acuity (DCNVA) (ETDRS high contrast) (photopic and mesopic) at 8AM.
- Percentage of subjects achieving improvements from Baseline to Day 8, Day 15, and Day 16 in BCDVA and DCNVA (photopic and mesopic) of greater than or equal to 1 line, 2 lines and 3 lines. For BCDVA, only the number of letters read is collected; this will be converted to lines as follows: 1 line = 3-7 letters read; 2 lines = 8-12 letters read; 3 lines = 13-17 letters read, etc. For DCNVA, only the logMAR value is collected; this will be converted to lines as follows: 1 line = 1.3 logMAR; 2 lines = 1.2 logMAR; 3 lines = 1.1 logMAR, etc. to 14 lines = 0.0 logMAR, 15 lines = -0.1 logMAR, 16 lines = -0.2 logMAR, and 17 lines = -0.3 logMAR.

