## 5.3. Randomization and Blinding

All eligible and consented subjects will be randomized in a 1:1 ratio to receive 1 % Nyxol or placebo. Once a subject is qualified for the study (Qualification/Baseline Visit) the subject is assigned a randomization number.

Rules for unblinding a subject for safety reasons are fully described in the protocol and not repeated herein this SAP.

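### The 'all eyes' secondary analyses treat a subject's two eyes as independent, so their standard errors and 95% confidence intervals are too narrow on average

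*SAP*

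**What the plan says.** SAP 4.2.2 and SAP 9.1 (Secondary Efficacy Endpoints) require the secondary endpoints to be analyzed for the study eye, the fellow eye and all eyes. The last of these pools the two eyes, giving "2 results per subject for any summary of all eyes if the endpoint was assessed for both the study eye and fellow eye".

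For continuous secondary endpoints, SAP 9.1 states that "the same ANCOVA for the primary efficacy endpoint will be used, with the respective Baseline included as the covariate". The primary model is specified as "treatment as a factor; and Baseline mean diurnal IOP as the covariate". For endpoints on the "percentage of subjects (or percentage of eyes) meeting certain criteria", it specifies a "logistic regression with treatment and Baseline included as independent factors". The promised output is least-squares means with standard errors, differences with 95% CIs and p-values for the ANCOVAs, and odds ratios with 95% CIs and p-values for the logistic models. SAP 7.2.1 lists baseline values as the only planned covariates.

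On the design, SAP 5.3 says "All eligible and consented subjects will be randomized in a 1:1 ratio", and Protocol 4.1 says "ALL TREATMENTS WILL BE ADMINISTERED TO BOTH EYES AND IOP WILL BE MEASURED IN BOTH EYES". Protocol 9.3.1 treats secondary p-values as descriptive.

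**The concern.** Treatment varies only between subjects. The primary ANCOVA has one row per subject, so its independence assumption is reasonable there. The all-eyes version keeps the same model but enters two rows per subject. Both rows come from the same person, on the same treatment, measured at the same visits. The model then counts about 72 independent observations where there are about 36 independent subjects.

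What is at stake is the stated precision of the pooled results for continuous IOP, pupil and acuity endpoints and for the responder thresholds. The IOP endpoints are also repeated in the two Baseline-IOP subgroups. The pooled interval would be printed beside valid study-eye and fellow-eye intervals and would look more precise than it is. SAP 3.2 foresees use of the results in regulatory submissions and manuscripts.

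**Working it through.** **Inputs from the documents.** 36 completers randomized 1:1, taken as 18 per arm; SD 3.0; two-sided 5% test (Protocol Section 1, Sample Size Justification). Two rows per subject, with treatment and Baseline as the only terms (SAP 9.1).

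**The plan's own figure.** 36 / (1 − 0.10) = 40 randomized, which reproduces. The 36 itself cannot be rebuilt because the effect size and power are redacted.

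**Assumption.** The documents give no between-eye residual correlation ρ, so a range is shown.

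**Formula.** Take n subjects per arm, two eyes each and residual variance σ², leaving the covariate aside.

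- Variance of the treatment difference if the rows are treated as independent: 2σ²/(2n) = σ²/n. SE = 3.0/√18 = 0.71.
- True variance: σ²(1 + ρ)/n. SE = 0.71 × √(1 + ρ).
- True/reported ratio: √(1 + ρ). It does not depend on the SD.

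**Simulation of the ANCOVA as written.** No treatment effect, 18 per arm, eye-specific baseline, assumed baseline between-eye correlation 0.7, 20,000 replicates per setting:

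| ρ | √(1+ρ) | True SE by formula | Simulated true/reported SE | Type I error | Coverage of 95% CI |
|---|---|---|---|---|---|
| 0.3 | 1.14 | 0.81 | 1.15 | 8.5% | 91.5% |
| 0.5 | 1.22 | 0.87 | 1.24 | 11.1% | 88.9% |
| 0.7 | 1.30 | 0.92 | 1.33 | 13.9% | 86.1% |
| 0.9 | 1.38 | 0.97 | 1.41 | 16.3% | 83.7% |

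At ρ = 0 the type I error is 5.0%, so there is no fault. A separately coded repeat with 10,000 replicates gave 8.5%, 11.0%, 14.4% and 16.2%; its reported SE stayed at about 0.70 to 0.71 whatever ρ was.

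**Sensitivity.**

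- 20 per arm: 8.4%, 11.2%, 13.6%, 16.6%.
- Higher-IOP eye chosen as study eye, with a 22–30 mmHg window (8,000 replicates): 8.9%, 11.0%, 13.7%, 16.2%.

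**Logistic model.** Latent-normal responder, 18 per arm, 4,000 replicates, fits with a finite odds ratio, ρ (latent) 0.3 to 0.9:

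| Response rate | Type I error |
|---|---|
| 50% | 7.5–14.3% |
| 30% | 6.9–13.3% |
| 20% | 5.9–12.4% |
| 15% | 4.2–8.7% |
| 10% | 2.2–4.3% |

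A separately coded repeat at about 50% response gave 5.7% to 14.0%. At 10% response the model SE was still too small on average (true/model 1.03 to 1.10), but the Wald test rejected less than 5% of the time.

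**Check of the remedies, 18 per arm, ρ 0.3 to 0.9 (type I error).**

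- ANCOVA on the two-eye mean: 4.8–5.2%.
- ANCOVA on the mean of observed eyes, 10% of subjects missing one eye: 4.8–5.4%.
- Subject random intercept by REML, t on 33 df as a stand-in for Kenward-Roger: 4.1–5.0%.
- GEE at 20–50% response: 2.5–3.5% with the Mancl-DeRouen correction, 3.3–4.4% with Kauermann-Carroll.

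**The case against.** **The method is inferred from silence.** The two-rows sentence speaks of summaries, the ANCOVA paragraph does not mention covariance, and the protocol's text on continuous secondary endpoints is redacted. However, SAP 9.1 is readable, orders analysis by all eyes, refers to percentages of eyes and names the model terms. Ordinary ANCOVA and logistic regression are its natural reading.

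**The logistic half is weaker.** This stands in part. At 10% response the nominal 5% test is not inflated, and the documents give no expected response rates. The number of affected thresholds is therefore unknown, and no inflation is claimed for rare responses.

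**The consequences are limited.** This also stands. All eyes is one of three parallel views, the other two do not have this error, the primary uses the study eye only, and secondary p-values are descriptive under the protocol. Against that, SAP 7.4.1 calls p ≤ 0.05 statistically significant in all tests. A 95% CI that covers about 89% (ρ = 0.5) is wrong whatever the status of its p-value.

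**The size is assumed.** Correct: only the direction is established, and it needs a positive ρ. A negative ρ would reverse it, but that is implausible for two eyes of one person under the same treatment.

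**Conclusion.** The point holds and should be fixed. As written, SAP 9.1 gives all-eyes ANCOVA standard errors and 95% CIs that are too narrow on average for any positive between-eye residual correlation. Over the assumed range 0.3 to 0.9, the SE is understated by a factor of 1.15 to 1.41. For responder endpoints, type I inflation is shown from about 20% response upward across that range, at 15% only toward the higher correlations, and not at 10%.

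The primary conclusion is not threatened, and the separate study-eye and fellow-eye analyses are sound. Day 16 all-eyes IOP is also outside the point if Protocol 7.2.6, which measures only the study eye that day, governs.

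**What to change.** In SAP 9.1, state one method for each type of all-eyes endpoint.

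- **Continuous endpoints.** The simplest choice is ANCOVA on the per-subject mean of the observed eyes, with the matching mean baseline. A subject with one observed eye contributes that eye's value and baseline. The alternative is a mixed model with one row per eye, fixed treatment and Baseline, a subject random intercept (or unstructured within-subject covariance) and Kenward-Roger degrees of freedom. Do not use an eye-within-subject random effect: with one row per eye it is confounded with the residual. In one simulated dataset at ρ = 0.7 it returned the naive SE of 0.816, against 1.109 with a subject intercept.
- **Eye-level responders.** Use logistic GEE clustered on subject with a named small-sample variance correction. Where an arm has no responding eyes, or all respond, report counts and percentages only, or a prespecified subject-level permutation test.

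A cheaper option is to report all eyes descriptively, without SEs, CIs or tests. That gives up inference on an endpoint the protocol names.

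The cost is one SAP paragraph and a few lines of SAS. Continuous all-eyes intervals become about 15–40% wider from the SE alone, or 17–43% once the fall from 69 to 33 residual df (72 − 3 against 36 − 3) is counted. The corrected GEE test is conservative, at 0.6–1.7% type I error for 10% response. Some thresholds will have no finite odds ratio: the chance that an arm has no responding eyes, or all respond, is 6–15% at a 10% rate and 32–49% at 5%.

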## **10. SAFETY ANALYSES**

All Safety analyses will be conducted using the Safety population. All safety analyses will be completed using the actual treatment a subject received. Observed case data will be used; no imputation will be performed for missing safety data except for the limited situations described in [Section 7.3.2](#).

### **10.1. Adverse Events**

Adverse events will be coded using MedDRA, Version 22.0.

Treatment-emergent adverse events (TEAEs) are defined as any adverse event that begins or worsens after initiation of the investigational product and through the subject's last study visit (study completion or early termination) or follow-up telephone call. Serious adverse events will be recorded from the date of informed consent, throughout the clinical trial.

If the onset of an AE is on or after the date of first dose of study medication, or increasing in severity after first dose of study medication, then the AE will be considered treatment-emergent.

Only TEAEs will be summarized; all AEs (TEAE, non-TEAE) will be included in a by-subject listing.

The number and percent of subjects with any TEAEs will be summarized by system organ class and preferred term by treatment group and overall. At each level of tabulation (ex. at the preferred term level) subjects will be counted only once if they had more than one such event reported during the AE collection period.

Note that in MedDRA, ocular events are coded to the SOC of “special senses”. Thus, using SOC in the summaries will provide a separation of ocular and non-ocular adverse events.

The following summary tables will be presented for TEAE data:

- Overall summary of TEAEs
- Summary table of TEAEs by SOC and PT
- Summary table of TEAEs by highest relationship level to study drug by SOC and PT (not related, possibly related, related)
- Summary table of TEAEs by maximum severity by SOC and PT (mild, moderate, severe)
- Summary table of serious TEAEs by SOC and PT
- Summary table of TEAEs leading to withdrawal from the study by SOC and PT
- Summary table of TEAEs leading to study medication discontinuation by SOC and PT

